#### 11.2 Immune-Mediated Adverse Events

Adverse events that meet the definition of Immune-Mediated AEs will be summarized similarly as described in Section 11.1.

#### 11.3 Clinical Laboratory Evaluations

This study uses a central laboratory assessment of all safety lab data. Local laboratory values that are clinically relevant will be added to the case report forms. All aggregate analyses of data will be done using only the central laboratory data, but the local laboratory data will be presented in patient level data listings.

Clinical laboratory evaluations include the continuous variables for hematology, serum chemistry, and urinalysis. The laboratory values will be presented in standard units. The ontreatment period with an onset date on or after the date of first dose of study medication until the date of the last oral study medication plus 28 days or date of last IV dose plus 5 months (ie, 152 days), whichever is the latest date. Laboratory values collected during the ontreatment period will be included in the summary tables. The laboratory values collected outside of the on-treatment period will only be presented in the data listings.

For visit-based summaries; the laboratory evaluations that are during the actual scheduled cycle visit (ie, EDC visit structure) will be used, otherwise, any unscheduled laboratory evaluations that are closest to and within the same actual scheduled cycle will be used. The data sets should highlight the value for the patient that was included in the summary table, wherever feasible. The summary tables and graphs will only display data if the number of observations is greater than 10 in each treatment arm.

The summary of laboratory data will include descriptive statistics of the maximum, minimum, and last value during the on-treatment period. Summaries using descriptive statistics of the change from baseline to the maximum, minimum, and last value during the on-treatment period will also be given.

Shifts from baseline to the maximum on-treatment toxicity grade (CTCAE Version 5.0 or later) for each lab parameter will be summarized.

Figures of the mean values over time with standard error bars will be presented for key safety laboratory parameters.

Confidential 42 of 52

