3.1.3 Double-blind Treatment Phase

The Double-blind Treatment Phase will continue in 28-day treatment cycles. The first dose of oral study treatment will be administered on Cycle 1 Day 1 and continue BID throughout the cycle as monotherapy; IV study drug will begin on Cycle 2 Day 1 (C2D1). Details on study drug administration are described in Section 5.5. During the Double-blind Treatment Phase, patients will come into the study site for a visit on Day 1 and Day 15 of Cycles 1 and 2, and on Day 1 of every cycle thereafter. Study treatment will continue until 24 months after initiating oral/IV combination study treatment, disease progression, or unacceptable toxicity, whichever happens first.

During the Double-blind Treatment Phase (continuous 28-day treatment cycles), patients will be monitored for safety and efficacy. Assessments will include AEs, physical examination, vital signs and weight measurement, central laboratory hematology, serum chemistry, and CA-125 measurement, concomitant medications, therapies and procedures, ECOG performance status, disease status assessment, ctDNA analysis, study drug administration and accountability, and PRO. ECGs and urinalysis will be performed as clinically indicated.

Blood samples will also be collected to determine whether any mutation identified is of germline or somatic origin and for PPK analyses.

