7.4 Treatment Phase

7.4.1 Day 1 of Cycle 1

The following procedures/assessments will be completed before study drug is administered:

- PRO using the TOI FACT-O and EQ-5D-5L instruments or other format, as appropriate;
- Physical examination;
- Weight;
- Vital Signs;
- Concomitant medications and procedures;
- ECOG performance status (Appendix 3);
- Hematology;
- Serum chemistry (fasting is not required);
- CA-125 measurement;
- Blood sample for ctDNA analysis;
- Blood sample for determining germline/somatic BRCA status (Cycle 1 only; if sample is not collected on Day 1 of Cycle 1, it should be collected as soon as possible thereafter);
- Dispensation of oral study drug;
- AE monitoring.

Oral study drug (rucaparib or oral placebo) will be dispensed to the patient in sufficient quantity to last until the next treatment cycle. Patients will ingest oral study drug BID at about the same times every day, as close to 12 hours apart as possible. Patients may take study drug with or without food (with a regular meal or within 30 minutes after a regular meal). Patients will record dosing information in their dosing diary.

Patients will be instructed to refrain from taking their morning daily dose of study drug at home on the day of their clinic visits because certain assessments must be performed prior to dosing.

7.4.2 Days 15 of Cycle 1 and 2

The following procedures will be completed:

- Vital Signs;
- Concomitant medications and procedures;
- ECOG performance status (Appendix 3);
- Hematology;

- Serum chemistry (fasting is not required);
- AE monitoring.

Patients will ingest oral study drug (rucaparib or placebo) BID at about the same times every day, at close to 12 hours apart as possible. Patients may take study drug with or without food. Patients will record dosing information in their dosing diary. Patients will be instructed to refrain from taking their morning daily dose of study drug at home on the day of their clinic visits because certain assessments must be performed prior to dosing.

7.4.3 Cycle 2 Day 1

The following procedures/assessments will be completed before study drug is administered:

- PRO using the TOI FACT-O and EQ-5D-5L instruments or other format, as appropriate;
- Physical examination;
- Weight;
- Vital Signs;
- Concomitant medications and procedures;
- ECOG performance status (Appendix 3);
- Hematology;
- Serum chemistry (fasting is not required);
- CA-125 measurement;
- Blood sample for ctDNA analysis;

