## 3 GENERAL ANALYSIS CONVENTIONS

Efficacy analyses will be analyzed in the ITT Population as described in Section 10 below.

All safety analyses will be based on the Safety Population, which consists of all patients who received at least 1 dose of protocol-specified treatment of oral study drug and/or IV study drug. Further, for safety analyses, patients randomized to either arm containing IV Nivolumab (ie, Arm A or Arm C) who never receive Nivolumab, will be analyzed in the analogous arm containing IV Placebo (ie, Arm B or Arm D, respectively).

Quantitative variables will typically be summarized using frequencies and percentages for appropriate categorizations and may also be summarized using descriptive statistics. For variables summarized with descriptive statistics, the following will be presented: N, mean, standard deviation, median, minimum, and maximum. Categorical variables will be presented using frequencies and percentages.

The Kaplan-Meier methodology will be used to summarize time-to-event variables. The 50th (median) percentile with the 95% CI will be summarized for each randomized treatment group. The stratified hazard ratio from the Cox proportional hazards model will be used to estimate the HR between the randomized treatment groups. The number of patients with events and the number of censored patients will also be presented.

The primary endpoint of invPFS, secondary endpoint of OS, bicrPFS (if applicable), ORR and exploratory analyses for the ITT population will be analyzed using the stratification factors of HRD classification, disease status, and timing of surgery. If the model does not converge or if there are only patients from a single treatment arm per stratum or if one or more of the strata contain few patients (eg, <5 patients) then the stratification factor of disease status will be omitted first, then timing of surgery, if necessary. Additionally, the Firth correction in the PHREG procedure will be used.

All data will be used to the maximum possible extent but without any imputations for missing data.

Baseline is defined as the last measurement on or prior to the first day of oral study drug administration or randomization date if the patient was never treated.

Results of all statistical analysis will be presented using 95% CIs and two-sided p-values. The significance level for ATHENA-COMBO is set at a one-sided p=0.0125 (two-sided p=0.025).

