#### **Liver Function Tests**

Baseline results for four LTFs (ALT, AST, ALP and bilirubin) will not receive a numeric grade (grade 1-5). They will be categorized in relation to the ULN (eg, <=ULN, >ULN-3xULN, >3xULN-5xULN). Shifts in grade from baseline to maximum on-treatment post-baseline for these events (alanine aminotransferase increased, alkaline phosphatase increased, aspartate aminotransferase increased, and blood bilirubin increased) will not be summarized.

Confidential 49 of 52

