#### 11.2 Clinical Laboratory Evaluations

Clinical laboratory evaluations include the continuous variables for hematology, and serum chemistry. The laboratory values will be presented in standard units. Summary tables and graphical presentations will only include the laboratory values that are deemed to be "on-treatment" to oral study drug as follows: All clinical laboratory values with an onset date on or after the date of first dose of oral study medication until the date of the last oral study medication plus 28 days. The laboratory values collected outside of the on-treatment period for oral study drug will only be presented in the data listings.

For visit-based summaries; the laboratory evaluations that are during the actual scheduled cycle visit (ie, EDC visit structure) will be used, otherwise, any unscheduled laboratory evaluations that are closest to and within the same actual scheduled cycle will be used. The data sets should highlight the value for the patient that was included in the summary table, wherever feasible. The summary tables and graphs will only display data if the number of observations is greater than 10 in each treatment arm.

The summary of laboratory data will include descriptive statistics of the maximum, minimum, and last value during the on-treatment period. Summaries using descriptive statistics of the change from baseline to the maximum, minimum, and last value during the on-treatment period will also be given.

Shift summary tables from baseline to the maximum on-treatment toxicity grade (CTCAE v5.0 or later) for each lab parameter will be summarized.

Figures of the mean values over time with standard error bars will be presented for key safety laboratory parameters.

This study uses a central laboratory assessment of all safety laboratory data. Local laboratory values that are clinically relevant or support eligibility will be added to the CRFs. All aggregate analyses of data will primarily be done using only the central laboratory data. The local laboratory data will be presented in patient level data listings. However, an additional maximum on-treatment toxicity grade shift from baseline grade may be presented using both local and central laboratory data.

Additional detail regarding clinical laboratory evaluations are provided in Appendix 2.Urinalysis results will be reported in patient level listings.

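### The laboratory on-treatment window opens on the date of the first dose, so a pre-dose Cycle 1 Day 1 sample is both the baseline and an on-treatment value

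*SAP*

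**What the plan says.** **Window.** ATHENA-COMBO SAP 11.3 starts the laboratory on-treatment period thus: "The ontreatment period with an onset date on or after the date of first dose of study medication". It adds: "Laboratory values collected during the ontreatment period will be included in the summary tables". ATHENA-MONO SAP 11.2 has the same rule for the oral drug: "All clinical laboratory values with an onset date on or after the date of first dose of oral study medication". Protocol 9.7.2 also starts on the date of first dose. For vital signs, MONO SAP 11.3 and Protocol 9.7.3 use the date, whereas COMBO SAP 11.4 counts from the first dose itself.

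**Baseline.** COMBO SAP section 3: "Baseline is defined as the last measurement on or prior to the first day of oral study drug administration". MONO SAP section 3 defines it the same way.

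**Sampling.** Protocol 3.1.3: "The first dose of oral study treatment will be administered on Cycle 1 Day 1". Protocol 7.4.1, for that visit: "The following procedures/assessments will be completed before study drug is administered". Its list includes hematology, serum chemistry and vital signs.

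**Outputs.** COMBO SAP 11.3: "Shifts from baseline to the maximum on-treatment toxicity grade (CTCAE Version 5.0 or later) for each lab parameter will be summarized". It also plans the on-treatment maximum, minimum and last value, and the change from baseline to each. The opening of section 11 plans laboratory summaries by worst grade.

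**The one restriction.** COMBO SAP Appendix B, Liver Function Tests, refers to "Shifts in grade from baseline to maximum on-treatment post-baseline for these events". It covers ALT, AST, ALP and bilirubin only, and says that those shifts will not be tabulated. MONO SAP Appendix 2 does the same.

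**The concern.** Baseline and on-treatment values should not share a record. Here both definitions include the first dosing day, and the planned sample on that day is taken before the drug. If the rule is programmed as written, the baseline value is one of the values from which the on-treatment maximum, minimum and worst grade are chosen.

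At stake is how the descriptive laboratory tables read. Patients are randomized within 8 weeks of the first day of their last chemotherapy cycle and may enter with Grade 2 anemia if hemoglobin is at least 9 g/dL (Protocol 4.2 and 4.3). An abnormality left over from chemotherapy could be tabulated as arising on study treatment, and a patient whose values only improved would show no improvement.

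**Working it through.** The plan states no figure to reproduce. The check applies its date rules.

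**Step 1: the overlap.** Number the first-dose date as day 1. Baseline is the last value with day ≤ 1; on-treatment means day ≥ 1. A sample dated day 1 satisfies both. No sentence in COMBO SAP 11.3 requires a post-dose time or removes the baseline record.

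**Step 2: what follows without assumptions.** Let *b* be the baseline value and *Gb* its grade. Let *m*, *M* and *Gp* be the minimum, maximum and worst grade of the later samples. With the baseline record included:

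- worst on-treatment grade = max(*Gb*, *Gp*) ≥ *Gb*
- change to minimum = min(*b*, *m*) − *b* ≤ 0
- change to maximum = max(*b*, *M*) − *b* ≥ 0

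For the shift table:

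| Later samples | Cell as written | Cell, post-baseline only |
|---|---|---|
| *Gp* > *Gb* | *Gb* to *Gp* | *Gb* to *Gp* |
| *Gp* = *Gb* | *Gb* to *Gb* | *Gb* to *Gb* |
| *Gp* < *Gb* | *Gb* to *Gb* | *Gb* to *Gp* |

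Only improvements move, and they move to the diagonal. Every worsening cell is identical. In the marginal count of worst grade 2 or higher, the patients added are those with *Gb* ≥ 2 and *Gp* < 2.

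**Step 3: a worked patient.** The values are assumed. Hemoglobin in g/L: screening 101, Cycle 1 Day 1 pre-dose 98, then 103, 106 and 110; lower limit of normal assumed 115. SAP cut-offs: Grade 1 from 100 to below the lower limit, Grade 2 from 80 to below 100.

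| | As written | Post-baseline only |
|---|---|---|
| Baseline grade | 2 | 2 |
| Worst on-treatment grade | 2 | 1 |
| Change to minimum | 98 − 98 = 0 | 103 − 98 = +5 |
| Change to maximum | 110 − 98 = +12 | 110 − 98 = +12 |

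**Step 4: which counts can be affected.** Entry requires ANC of at least 1.5 and platelets above 100 (× 10⁹/L). On the SAP cut-offs (Grade 2 below 1.5 and below 75) both are at most Grade 1 at screening. Hemoglobin may be 90 to below 100 g/L, which is Grade 2. Among these three, a pre-dose Grade 2 is therefore chiefly a hemoglobin matter, unless a count falls between screening and Cycle 1 Day 1.

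**Step 5: possible size.** The hemoglobin distributions below are assumptions; none is in the documents.

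- *Set 1.* Baseline mean 112, SD 11, floored at 90; within-patient SD 6. Share of patients whose worst anemia grade, of any grade, is set by the baseline sample: 18% with 3 later samples and a rise of 8 g/L; 0.5% with 26 samples and the same rise; 1.3% with 3 samples and no drift; about 0% with a fall of 8 or 20 g/L. The any-grade share is an upper bound for Grade 2 or higher.
- *Set 2.* Placebo-like: Cycle 1 Day 1 mean 108 to 113, SD 10; within-patient SD 4; recovery of 12 to 18 g/L with time constant 28 to 56 days; 14 later samples; screening value at least 90. Worst anemia of Grade 2 or higher: 2 to 17% from later samples against 10 to 24% as written, a difference of about 4 to 14 points within scenarios.

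**The case against.** **Loose wording, not a chosen analysis.** Appendix B says post-baseline, COMBO vital signs start at the dose itself, and the laboratory sentence borrows the adverse-event language of onset dates. A programmer may well exclude the flagged baseline record. The intent is plausible, but no sentence says so for hemoglobin, neutrophils, platelets or creatinine, and literal programming gives the results above.

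**A reader might infer that the rule hides rucaparib's hematologic toxicity.** The documents do not support that. Worsening shifts are the same under both rules, and a 2-to-2 patient is shown with baseline Grade 2. Where the drug lowers counts, later values set the worst grade and nothing changes. What remains is some inflation of the marginal worst-grade count in arms where values recover.

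**A reader might take 4 to 14 points as the expected inflation.** It rests on an assumed recovery and noise level; other assumptions give about 0. Nothing in the documents shows that the Cycle 1 Day 1 value is often the lowest.

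**The main comparison is little affected.** COMBO compares A with B, and both receive rucaparib. B against D belongs to MONO, whose primary analysis was performed on 23 March 2022 (COMBO SAP 3.5). Both points stand. Section 11 of the COMBO SAP nevertheless presents safety for all four arms.

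**Not every sample overlaps.** One drawn on a day before the first dose is baseline only. That is correct, but Protocol 7.4.1 plans assessments and dispensing at the same visit, so a shared date is the ordinary case.

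**Conclusion.** The point holds in a limited form. For every patient whose baseline is a Cycle 1 Day 1 sample dated on the first-dose day, the written rule puts the baseline value into the on-treatment set. The three bounds in step 2 follow with no further assumption: improvements are lost, and worsening is shown correctly. The worst-grade summary can also count a pre-dose abnormality, chiefly Grade 2 anemia, as on-treatment.

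The size cannot be read from the documents. It depends on how far values recover and how many later samples there are. The illustrations run from about 0 to well over 10 percentage points, and matter mainly for the arms without rucaparib (C and D). Grade shifts for the four liver tests are not affected because they are not tabulated, but their maximum, minimum and change summaries are.

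This concerns descriptive safety tables only. Alpha, power and the efficacy tests are untouched. It is worth correcting because the stated rule, followed exactly, gives a wrong table.

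**What to change.** State in COMBO SAP 11.3 that the on-treatment maximum, minimum, last value and worst grade use only post-baseline records: those dated after the first-dose date, or timed after the first dose on that date, up to the existing end of the window. Exclude the record flagged as baseline.

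Align Protocol 9.7.2 (laboratory) and 9.7.3 (vital signs), which carry the same date rule; changing the SAP alone would leave it at odds with the protocol. Make the same change in MONO SAP 11.2 and 11.3 for any later outputs, since that primary readout is already done.

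The cost is one sentence in each place and a post-baseline flag in the laboratory and vital-signs datasets. No new data are needed.

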Elevations in ALT, AST, and creatinine are commonly observed in patients receiving rucaparib and typically are observed beginning with Day 15 of the first cycle of treatment with rucaparib. The ALT/AST elevations typically peak after two weeks of dosing and are generally not accompanied by substantial concomitant elevation in bilirubin or alkaline phosphatase. There have been no cases of Hy's law observed across the clinical development program, and based on the data available to date, rucaparib does not appear to be associated with drug induced liver injury. In addition, mean creatinine values increase soon after initiation with rucaparib treatment but subsequently plateau. Creatinine elevation resolves with dose holds of rucaparib and recurs with rechallenge. Rucaparib associated creatinine elevation has not been associated with evidence or reports of permanent renal impairment. The increases in creatinine with rucaparib treatment is likely due to inhibition of MATE1/2K

renal transporters.⁴⁸ Elevations in ALT, AST, and creatinine are not typically observed with nivolumab treatment, however elevations in any of these laboratory parameters can be early signs of immune-mediated hepatitis or nephritis. Since Cycle 1 will only include oral study drug, this allows for Cycle 1 laboratory values to be assessed prior to initiation of the oral/IV study drug combination and ultimately should facilitate more accurate attribution to oral or IV study drug so the proper AE management algorithm may be followed.

Additional details on the safety profile of nivolumab and rucaparib, including results from other clinical studies, are also available in the respective drug IBs.

To assure an ongoing favorable risk/benefit assessment for participants enrolled into the present study, the following measures will be employed throughout the conduct of the study:

- Oral study drug administration will begin 28 days (1 cycle) prior to IV study drug administration to explore the hypothesis that priming the TMB with monotherapy rucaparib will enhance the activity in combination with nivolumab. It will also allow the baseline safety profile for oral drug to be established, which will guide appropriate AE management, if needed, during combination therapy.
- Institution of an Independent Data Monitoring Committee (IDMC) to provide independent oversight of safety, study conduct, and efficacy including regular and systematic reviews of safety data by treatment arm.

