Note: Rucaparib may cause transient AST and/or ALT elevations (without increased total bilirubin) at Cycle 1, Day 15 that begin to resolve by Day 29, even with continued rucaparib dosing.

Grade 2 or 3 colitis or diarrhea

- Grade 3 pancreatitis with symptoms. Grade 3 increased amylase or lipase without signs or symptoms of pancreatitis does not require dose delay
- Grade 2 rash covering > 30% body surface area or Grade 3 drug-related skin AE. Suspected Stevens-Johnson Syndrome (SJS), toxic epidermal necrolysis (TEN), or drug reaction with eosinophilia and systemic symptoms (DRESS)
- Endocrinopathies met the following criteria:
 - Grade 2 adrenal insufficiency.
 - Grade 2 or 3 hyperglycemia requiring initiation or change in daily management.
 - Grade 1-3 hypophysitis/hypopituitarism that is symptomatic and also associated with corresponding abnormal lab and/or pituitary scan.
 - Grade 2 or 3 hyperthyroidism or hypothyroidism.
- Grade 2 uveitis.
- Grade 2 neurological (other than Guillain-Barre Syndrome [GBS], myasthenia gravis [MG], encephalitis, or myelitis).
- Any grade of encephalitis or myelitis. After workup for differential diagnosis, (ie, infection, tumor-related), if it is not drug related, then dosing may resume when AE resolves.
- Myocarditis with symptoms induced from mild to moderate activity or exertion.
- Other Grade 3 drug-related AE with first occurrence lasting ≤ 7 days.
- Grade 3 drug-related laboratory abnormality (not listed above), with the following exceptions:
 - Grade 3 lymphopenia or Grade 3 increased amylase or lipase without signs or symptoms of pancreatitis does not require dose delay.
 - Grade 3 thrombocytopenia > 7 days or associated with bleeding requires for dose discontinuation.
 - AST, ALT, and/or total bilirubin elevations with a range of AST or ALT > 5 × ULN or total bilirubin > 3 × ULN, regardless of baseline value, will require dose delay or discontinuation. (See Section 5.6.4.2)*
- Any AE, laboratory abnormality, or intercurrent illness that, in the judgment of the investigator, warrants delaying the dose of study medication.

Participants who require dose hold should be re-evaluated weekly or more frequently if clinically indicated and resume dosing during the next scheduled dosing window (Cycle X, Day 1 ± 3 days) after re-treatment criteria are met (Section 5.6.2).

Please refer to Appendix 8: AE Criteria for Delay, Resume and Discontinue of Nivolumab.

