- Disease status (no residual disease vs residual disease); and
- Timing of surgery (primary surgery vs interval debulking).

Randomization to study treatment must occur within 8 weeks following a patient's first day of the last cycle of chemotherapy.

During the Double-blind Treatment Phase (continuous 28-day treatment cycles), the double blinded oral study treatment will be administered on Day 1 of Cycle 1 and continue BID throughout the cycle as monotherapy. IV study drug administration will begin on Day 1 of Cycle 2 during the Double-blind Treatment Phase. Patients will have clinic visits on Day 1 and Day 15 of Cycles 1 and 2, and on Day 1 of every cycle thereafter. Study treatments will continue until 24 months after planned initiation of oral/ IV combination study treatment (C2D1), disease progression, unacceptable toxicity, or withdrawal of participant consent, whichever happens first.

During the Treatment Phase patients will be monitored for safety and efficacy. Assessments will include AEs, physical examination, vital signs and weight measurement, central laboratory hematology, serum chemistry, and CA-125 measurement, concomitant medications, therapies, and procedures, ECOG performance status, disease status assessment, ctDNA analysis, study drug administration and accountability, and PRO. ECGs and urinalysis will be performed as clinically indicated. Blood samples will also be collected to determine whether any mutation identified is of germline or somatic origin.

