#### 11 SAFETY ANALYSIS

Safety and tolerability is one of the secondary study objectives. Overall safety and tolerability will be measured by the incidence of adverse events, serious adverse events, adverse events leading to discontinuation, deaths, specific laboratory abnormalities (worst grade) and changes from baseline.

The safety analyses will be presented for the safety population presenting the data for each treatment group separately (Arm A [rucaparib and nivolumab], Arm B [rucaparib], Arm C [nivolumab], and Arm D [placebo]). The analyses will be presented by the actual treatment given. Patients randomized to either treatment group containing IV Nivolumab (ie, Arm A or Arm C) who never receive Nivolumab, will be analyzed in the analogous treatment group containing IV Placebo (ie, Arm B or Arm D, respectively).

Summary tables are based on data that are found to be "on-treatment"/ "treatment-emergent" for the oral or IV study drug as outlined in the below sections.

All safety data which is considered treatment-emergent will be summarized. Treatment-emergent is defined as safety data with an onset date on or after the date of first dose of study medication until the date of last dose of oral study drug plus 28 days or date of last IV dose plus 5 months (ie, 152 days), whichever is the latest date.

Descriptive statistics of safety will be presented using the NCI CTCAE v5.0. All AEs, drug-related adverse events, serious adverse events (SAEs) and drug-related SAEs will be tabulated using the worst grade per NCI CTCAE v5.0 by system organ class and preferred term. On-study lab parameters including hematology, coagulation, chemistry, liver function, thyroid, adrenal and renal function will be summarized using worse grade by NCI CTCAE v5.0.

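### COMBO SAP worst-value laboratory tables do not isolate time on IV drug: ALT/AST pool the oral-only cycle, creatinine keeps a pre-oral baseline, and never-nivolumab patients move only from A to B

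*SAP*

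**What the plan says.** **Window and summaries.** COMBO SAP 11.3 defines the laboratory window by "The ontreatment period with an onset date on or after the date of first dose of study medication" and closes it 28 days after the last oral dose or 5 months after the last IV dose, whichever is later. Over that window, "The summary of laboratory data will include descriptive statistics of the maximum, minimum, and last value during the on-treatment period"; changes from baseline to those values are also given. Section 11 adds that laboratory parameters, including liver and renal function, "will be summarized using worse grade by NCI CTCAE v5.0".

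**Baseline.** COMBO SAP section 3: "Baseline is defined as the last measurement on or prior to the first day of oral study drug administration".

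**IV start.** COMBO SAP 2.2: "IV study drug administration will begin on Day 1 of Cycle 2 during the Double-blind Treatment Phase".

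**Expected rucaparib effects.** Protocol 1.2: "The ALT/AST elevations typically peak after two weeks of dosing". Protocol 5.6.1.2: "Rucaparib may cause transient AST and/or ALT elevations (without increased total bilirubin) at Cycle 1, Day 15". Protocol 1.2 also says that bilirubin and alkaline phosphatase generally do not rise substantially with ALT/AST, and that mean creatinine rises soon after the start and then levels off. For creatinine-based IV holds (5.6.1.2) and the renal algorithm (Appendix 7), the protocol's reference is the value before the first IV dose.

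**Grouping.** COMBO SAP sections 3 and 11: patients randomized to a nivolumab arm "who never receive Nivolumab, will be analyzed in the analogous treatment group containing IV Placebo". The protocol synopsis (Safety Analyses) and section 9.7 summarize safety by randomized group.

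**The concern.** COMBO has to describe what nivolumab adds to rucaparib. Protocol 1.2 warns that ALT, AST and creatinine elevations can be early signs of immune-mediated hepatitis or nephritis, and gives better attribution to oral or IV drug as a reason for the oral-only cycle. The planned worst-value tables do not use that design feature. None of them starts at the first IV dose, and none refers creatinine to its pre-IV value. The grouping rule adds a second difficulty: patients who never start IV drug, from both arms, end up in Arm B, and none remain in Arm A. At stake is how clearly the descriptive safety tables show nivolumab's contribution. No tested endpoint is involved.

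**Working it through.** The plan states no rate or power for these summaries, so there is no figure to reproduce. All rates below are assumptions. The arm size of 400 is from COMBO SAP 2.2.

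**1. ALT/AST: effect of the window.** Let c be the probability of reaching a grade in Cycle 1, equal in A and B because treatment is identical until Cycle 2 Day 1. Let a and b be the probabilities of reaching it after IV start, with subscript 1 or 0 for patients with or without a Cycle 1 event.

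- Post-IV excess = (1 - c)(a0 - b0) + c(a1 - b1)
- Planned (pooled) excess = (1 - c)(a0 - b0)

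The planned table loses c(a1 - b1), the excess among patients who already had a Cycle 1 event. If Cycle 1 and later events are independent, the planned excess is (1 - c)(a - b).

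With a = 10%, b = 5% and SE = sqrt[A(1 - A)/400 + B(1 - B)/400]:

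| Cycle 1 rate c | Arm A | Arm B | Excess, points (95% CI) |
|---|---|---|---|
| 0 (post-IV table) | 10.0% | 5.0% | 5.0 (1.4 to 8.6) |
| 2% | 11.8% | 6.9% | 4.9 (0.9 to 8.9) |
| 5% | 14.5% | 9.75% | 4.8 (0.2 to 9.3) |
| 10% | 19.0% | 14.5% | 4.5 (-0.7 to 9.7) |
| 20% | 28.0% | 24.0% | 4.0 (-2.1 to 10.1) |
| 30% | 37.0% | 33.5% | 3.5 (-3.1 to 10.1) |

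The loss is 2-5% at Cycle 1 rates of 2-5%, as might apply to a rare high grade, and 30% at a rate of 30%.

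Independence matters. With a = 15%, b = 8%, c = 20% and correlated latent normal variables for the two periods, the loss is 5% at correlation -0.5, 20% at 0 and 39% at 0.5.

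**2. ALT: one patient.** Normal pre-oral ALT; 4.5 x ULN on Cycle 1 Day 15; 1.5 x ULN before the first infusion; 4.0 x ULN in Cycle 5. Under COMBO SAP Appendix B, 4.5 and 4.0 x ULN are both Grade 2 (3-5 x ULN, normal baseline). Maximum, change to maximum and worst grade equal those of a patient with only the Cycle 1 rise. A post-IV summary shows 4.0 x ULN, which is 4.0/1.5 = 2.7 times the pre-IV value.

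**3. Creatinine: effect of the baseline.** Suppose 20% of both arms pass a threshold relative to the pre-oral baseline in Cycle 1 and stay above it, and 10% (A) or 5% (B) of the rest pass it after IV start.

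- Planned window: 0.20 + 0.80 x 0.10 = 28.0% vs 0.20 + 0.80 x 0.05 = 24.0%, excess 4.0 points.
- Window from first IV dose, same baseline: the 20% on the plateau still count, so again 28.0% vs 24.0%, excess 4.0 points.

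Moving the window therefore changes nothing; the reference value has to change. A patient going from 1.6 to 2.9 x BASE after IV start stays Grade 2 in Appendix B (1.5-3 x BASE) provided 3 x ULN is not exceeded. The maximum moves, but only the ratio to the pre-IV value, 2.9/1.6 = 1.8, shows that the rise came after IV start.

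**4. Moving never-nivolumab patients.** Keep c = 20% overall, a = 10%, b = 5%. A fraction f of each arm never starts IV drug and has Cycle 1 rate r. Those who start have ps = (0.20 - r f)/(1 - f).

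- SAP Arm A = ps + 0.10(1 - ps), on 400(1 - f) patients
- SAP Arm B = [400(1 - f)(ps + 0.05(1 - ps)) + 2 x 400 f r] / [400(1 + f)]
- As-randomized excess = (1 - f)(1 - ps) x 5 points, which is 3.8 to 4.0 here

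| r | SAP excess, points, at f = 2% / 3% / 5% |
|---|---|
| 0 | 4.9 / 5.4 / 6.3 |
| 20% | 4.2 / 4.2 / 4.4 |
| 60% | 2.6 / 1.9 / 0.5 |

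For f = 5%, r = 0: ps = 0.20/0.95 = 0.211; Arm A 28.9%; Arm B 380 x 0.25/420 = 22.6%; excess 6.3. The SAP and as-randomized figures agree at r of about 26%. Below that the rule exaggerates the nivolumab excess; above it the rule hides part of it. The documents give neither r nor f.

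**The case against.** **A vs B is a randomized contrast.** Before any patient is moved, the arms differ only in IV drug, so an excess over the whole window is already attributable to nivolumab. Worst value over the whole course is a legitimate summary. That stands, and is why the existing tables should stay. It does not supply the post-IV comparison.

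**The plan follows the protocol.** Baseline and window match Protocol 9.1 and 9.7.2. That stands; there is no conflict on those two items. The grouping does depart from the protocol.

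**Analysis by treatment received is a stated choice.** Arm B patients who never receive IV placebo took rucaparib alone and already sit in the rucaparib-only group, so no counterpart rule is missing. That stands as a defense of the labels. It does not remove the imbalance: never-starters from both arms are counted in B.

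**Other outputs separate the periods.** Under Protocol 8.5 a laboratory abnormality becomes an AE when it leads to action on study drug. The ALT patient above is in the range where IV drug is held if the rise is drug-related (5.6.1.2). A hold would put her in the IV-interruption table and possibly the IV-related and immune-mediated tables (COMBO SAP 11.1, 11.2). By-visit summaries and mean plots (11.3) show Cycle 1 separately, and IV delays are tabulated (7.1). This is substantial mitigation. Its limits are that AE tables depend on reporting, attribution or action, and mean plots can miss a few patients with large rises. Appendix B drops liver grade shifts, so for ALT/AST the point concerns maximum, change to maximum and worst grade.

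**A reader might infer that the window masks every liver test and creatinine.** The documents do not support that: bilirubin and alkaline phosphatase are expected to rise little in Cycle 1, and creatinine plateaus.

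**Conclusion.** The point holds in limited form.

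- **ALT/AST:** pooling the oral-only cycle can dilute the A-minus-B excess in worst values. The loss equals the Cycle 1 rate if the periods are independent, and is smaller or larger under negative or positive correlation. It is small for rare high grades. The direction assumes that nivolumab raises the later rate among patients with a Cycle 1 event.
- **Creatinine:** the pre-oral baseline is the cause. Changing the window alone would not help.
- **Grouping:** a one-sided selection of unknown sign that departs from the protocol's randomized grouping.

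A reader might conclude that nivolumab liver or kidney toxicity will be concealed, or that the trial's inference is biased. Neither follows. The Cycle 1 rates, and the number and event rates of patients who never start IV drug, are not in the documents; several other outputs would show such events; and these tables are descriptive, with no test attached. The intervals in the working show precision only. Importance is minor; the change is worth making because it is cheap.

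**What to change.** Keep the current tables. In COMBO SAP 11.1 and 11.3 add, for A vs B in patients with at least one IV dose (nivolumab or IV placebo), from first IV dose to the end of the on-treatment period:

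- worst ALT and AST by multiples of ULN, with total bilirubin so that concurrent elevations can be seen;
- worst creatinine as a ratio to the last value before the first IV dose;
- TEAEs with onset on or after the first IV dose.

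Do not use the pre-IV value as the CTCAE baseline for liver tests. Under Appendix B, ALT going from 0.7 (pre-oral) to 3 (pre-IV) to 6 x ULN is Grade 3 from the normal pre-oral baseline, but 6/3 = 2.0 x BASE, Grade 1, from the abnormal pre-IV one.

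Report how many patients move from A to B and from C to D, and add an as-randomized sensitivity table for key safety summaries. Post-IV tables for C vs D are optional: neither arm receives rucaparib, so there is no rucaparib Cycle 1 rise to remove.

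The cost is SAP wording and a few descriptive tables from data already collected. The new tables leave out patients who never start IV drug, so they supplement the existing ones. Since A and B are treated identically under blinding before Cycle 2 Day 1, the groups that start IV drug should remain comparable.
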